4.3.1 Women of child-bearing potential

A woman is considered to be of child-bearing potential unless she meets at least one of the following criteria:

- Previous bilateral salpingo-oophorectomy or hysterectomy
- Premature ovarian failure confirmed by a specialist
- XY genotype, Turner syndrome, uterine agenesis
- Postmenopausal, defined as 12 consecutive months with no menses without an alternative medical cause (ICH M3 definition)

Confidential

WOCBP participating in the study must agree to use one of the following reliable MOC from the screening visit and up to the protocol defined EOS:

- Two MOC, one from Group 1 and one from Group 2, defined as follows:
 - Group 1: Oral, implantable, transdermal or injectable hormonal contraceptives or intrauterine devices. If a hormonal contraceptive is chosen from this group, it must be taken for at least 1 month prior to enrollment
 - Group 2: Female or male condoms, diaphragm or cervical cap

OR

- True abstinence from intercourse with a male partner only when this is in line with the preferred lifestyle of the subject

OR

- Permanent female sterilization (tubal occlusion/ligation at least 6 weeks prior to screening)

OR

- Sterilization of the male partner with documented post-vasectomy confirmation of the absence of sperm in the ejaculate

4.4 Exclusion criteria

Subjects must not fulfill any of the following exclusion criteria. It is not permitted to waive any of the criteria for any subject:

Cardiovascular

1. Resting HR < 50 bpm measured by 12-lead ECG at enrollment (prior to study drug administration).
2. Myocardial infarction within 24 weeks prior to screening or ongoing unstable ischemic heart disease.
3. Cardiac failure (NYHA class III or IV) or any severe cardiac disease at time of screening.
4. History or presence of valvular heart disease associated with symptoms or hemodynamic change.
5. History or presence of cardiac rhythm disorders (e.g., sino-atrial heart block, symptomatic bradycardia, atrial flutter or atrial fibrillation, ventricular arrhythmias, cardiac arrest).

6. Presence of an increased QT corrected for HR on the basis of Fridericia's formula (QTcF) interval > 470 ms (females), > 450 ms (males) measured by 12-lead ECG at screening or pre-dose on Day 1.
7. History of syncope associated with cardiac disorders.
8. Systemic arterial hypertension not controlled by medication as judged by the investigator.

Hematologic

9. Hemoglobin (Hb) < 8.0 g/dL or need for red blood cell transfusion at screening.
10. Absolute neutrophil count $< 1.5 \times 10^9/L$ (< 1500 cells/mm 3) at screening.
11. Absolute lymphocyte count $< 0.5 \times 10^9/L$ (< 500 cells/mm 3) at screening.
12. Platelet count $< 50 \times 10^9/L$ ($< 50,000$ cells/mm 3) or need for platelet transfusion at screening.

Hepatic

13. ALT and/or AST ≥ 3.0 -fold the upper limit of normal (ULN) at screening.
14. Total bilirubin (TBL) > 1.5 -fold ULN (unless in the context of known Gilbert's Syndrome) at screening.
15. Known chronic liver or biliary disease that is not due to chronic GVHD.

Infection and infection risk

16. Active or uncontrolled bacterial, viral, or fungal infection (except onychomycosis and dermatomycosis); positive hepatitis B surface antigen or hepatitis C antibody tests at screening.
17. Cytomegalovirus (CMV) disease, including CMV pneumonia, CMV retinitis, and CMV gastroenteritis and/or subjects meeting institutional criteria for systemic therapy for CMV reactivation. (Subjects with positive CMV serology and/or CMV reactivation are not excluded if they do not have CMV disease and do not require systemic therapy.)
18. Active or latent tuberculosis (TB), as assessed by chest X-ray (CXR) performed at screening or within 90 days prior to screening, and interferon gamma release assay (QuantiFERON-TB-Gold[®]) at screening, except if there is documentation that the subject has received adequate treatment for TB previously.
19. Congenital or acquired severe immunodeficiency or known human immunodeficiency virus (HIV) or positive HIV testing at screening.

Malignancy

20. New or recurrent malignancy or minimal residual disease.

Metabolic

21. Type 1 or 2 diabetes that is poorly controlled according to investigator judgment or diabetes complicated with organ involvement such as nephropathy or retinopathy.

Ophthalmologic

22. Presence of macular edema.

Pregnancy and breastfeeding

23. Breastfeeding, pregnant women or women planning to become pregnant during the study.

Pulmonary

24. Subjects with a clinically significant pulmonary condition including asthma and chronic obstructive pulmonary disease (COPD) that is insufficiently controlled according to investigator judgment.

25. Subjects with diagnosed BOS.

26. Subjects with any hospitalization due to a clinically significant pulmonary condition including asthma or COPD exacerbation within 24 weeks prior to screening (with the exception of a fully resolved pulmonary infection).

27. Subjects with abnormal PFTs: $FEV_1 < 60\%$ of predicted normal value or $FEV_1/forced vital capacity (FVC) < 0.7$ at screening.

Renal

28. Severe renal insufficiency defined as a calculated creatinine clearance $< 30 \text{ mL/min}/1.73 \text{ m}^2$ (Cockcroft-Gault) at screening.

Treatments

29. Systemic glucocorticoids at prednisone-equivalent dose $> 1.0 \text{ mg/kg/day}$ at screening.

30. Treatment within 15 days prior to enrollment with:

- Azathioprine
- β -blockers, diltiazem, verapamil, digoxin, digitoxin or any anti-arrhythmic or HR-lowering systemic therapy (a non-exhaustive list of drugs provided in Appendix 4)
- CsA, TAC, MMF, MPS, EVL, SRL (with the exception of any therapy serving as a mandatory concomitant therapy, as per inclusion criterion 4 and Section 5.2).
- Extracorporeal photopheresis
- Isotretinoin

- Thalidomide

31. Treatment within 30 days prior to enrollment with:

- Acitretin
- Cyclophosphamide
- Etanercept
- Imatinib
- Vaccination with live vaccines

32. Treatment within 45 days prior to enrollment with:

- Pulse methylprednisolone
- MTX (with the exception if MTX serves as a mandatory concomitant therapy, as per inclusion criterion 4 and Section 5.2).

33. Treatment within 60 days prior to enrollment with:

- Basiliximab

34. Treatment within 24 weeks prior to enrollment with:

- Anti-lymphocyte globulin (ALG)
- Anti-thymocyte globulin (ATG)
- Belimumab
- Mesenchymal stem cell therapy
- Ofatumumab
- Pentostatin
- Rituximab

35. Treatment within 36 weeks prior to enrollment with:

- Hydroxychloroquine

36. Treatment within 48 weeks prior to enrollment with:

- Alemtuzumab
- Clofazamine

37. Treatment with any IS or immunomodulatory drug or technology not identified in items 30 to 37, unless discussed with the sponsor to determine appropriate washout. Chemotherapy and radiation for conditioning treatment leading up to the stem cell transplant and growth factors are exempt and do not have to be discussed with the sponsor.

Confidential

Other Categories

38. Karnofsky Performance Score (KPS) < 60%.
39. Known history of clinically significant drug or alcohol abuse.
40. Known allergy to any of the ponesimod formulation excipients.
41. Any other clinically relevant medical or surgical condition, which, in the opinion of the investigator, would put the subject at risk by participating in the study.
42. Subjects unlikely to comply with protocol, e.g., uncooperative attitude, inability to return for follow-up visits, or known likelihood of not completing the study including mental condition rendering the subject unable to understand the nature, scope, and possible consequences of the study.

4.5 Medical history

Relevant medical history, as defined below, must be recorded in the eCRF:

- Chronic medical conditions at any time in the past.
- Cardiac, cardiovascular, pulmonary, immune, hepatic, and eye conditions at any time in the past.
- New, significant acute medical conditions in the past 12 months prior to the study start.
- Smoking status

HSCT and GVHD history, as defined below, must be recorded in the eCRF including:

- Diagnosis leading to HSCT (acute myelogenous leukemia, acute lymphoblastic leukemia, aplastic anemia, chronic lymphocytic leukemia, chronic myelogenous leukemia, hodgkin's lymphoma, multiple myeloma, myelodysplastic syndrome, myeloproliferative disorder, non-hodgkins lymphoma, other cancer, other non-malignant disease).
- Date of HSCT
- HSCT-conditioning regimen (myeloablative, non-myeloablative, reduced-intensity, none)
- HSCT-conditioning agents (ALG, ATG [for ALG, ATG, specify source: horse, rabbit, other]; busulphan, oral; busulphan, i.v.; campath; carmustine; cyclophosphamide; cytarabine/AraC; etoposide; fludarabine; melphalan $\leq 140 \text{ mg/m}^2$; melphalan $> 140 \text{ mg/m}^2$; total body irradiation $\leq 500 \text{ cGy}$ single dose / $\leq 800 \text{ cGy}$ fractionated; total body irradiation $> 500 \text{ cGy}$ single dose / $> 800 \text{ cGy}$ fractionated; no conditioning; other)
- HSCT source (bone marrow, mobilized peripheral blood stem cells, cord blood, double cord)

- Allogeneic donor type (syngeneic; HLA-identical sibling; HLA-matched other relative; HLA-mismatched relative – 1 antigen mismatched [haplo-identical (yes, no)]; HLA-mismatched relative – ≥ 2 mismatched [haplo-identical (yes, no)]; matched unrelated donor; mismatched unrelated donor).
- For double cord only, second donor type (syngeneic; HLA-identical sibling; HLA-matched other relative; HLA-mismatched relative – 1 antigen mismatched [haplo-identical (yes, no)]; HLA-mismatched relative – ≥ 2 mismatched [haplo-identical (yes, no)]; matched unrelated donor; mismatched unrelated donor).
- Donor gender (male, female; choose two genders if double cord: male/female, male/male, female/female).
- Date of onset and resolution of acute GVHD.
- Acute GVHD diagnosis based on evidence from a biopsy (yes, no).
- Maximum overall grade of acute GVHD: I, II, III, or IV.
- Maximum severity of skin involvement, acute GVHD
 - No skin acute GVHD / rash not attributable to acute GVHD
 - Stage 0 – no rash
 - Stage 1 – maculopapular rash, < 25% of body surface
 - Stage 2 – maculopapular rash, 25–50% of body surface
 - Stage 3 – generalized erythroderma
 - Stage 4 – generalized erythroderma with bullae formation and desquamation
- Maximum severity of lower gastrointestinal tract, acute GVHD
 - No lower GI acute GVHD / diarrhea not attributable to acute GVHD
 - Stage 0 – no diarrhea
 - Stage 0 – diarrhea ≤ 500 mL/day
 - Stage 1 – diarrhea > 500 but ≤ 1000 mL/day
 - Stage 2 – diarrhea > 1000 but ≤ 1500 mL/day
 - Stage 3 – diarrhea > 1500 mL/day
 - Stage 4 – severe abdominal pain, with or without ileus
- Maximum severity of upper gastrointestinal tract, acute GVHD

- No upper GI acute GVHD / persistent nausea or vomiting not attributable to acute GVHD
 - Stage 0 – no persistent nausea or vomiting
 - Stage 1 – persistent nausea or vomiting
 - Maximum severity of liver involvement, acute GVHD
 - No liver acute GVHD / bilirubin level not attributable to acute GVHD
 - Stage 0 – bilirubin < 2.0 mg/dL
 - Stage 1 – bilirubin 2.0–3.0 mg/dL
 - Stage 2 – bilirubin 3.1–6.0 mg/dL
 - Stage 3 – bilirubin 6.1–15.0 mg/dL
 - Stage 4 – bilirubin > 15.0 mg/dL
- Other clinical involvement, acute GVHD (lung, other, none).
- Current and past acute GVHD treatments (ALG, ATG [for ALG, ATG, specify source: horse, rabbit, other]; glucocorticoids, systemic; glucocorticoids, topical; CsA; extra-corporeal photopheresis; tacrolimus [TAC]; anti-CD25 [zenapax, daclizumab, anti-Tac]; campath; etanercept; infliximab; other *in vivo* monoclonal antibody; *in vivo* immunotoxin; MTX; MMF; MPS; SRL; EVL; ursodiol; other agent).
- Date of onset of chronic GVHD
- Onset of chronic GVHD was:
 - Progressive (acute GVHD progressed directly to chronic GVHD)
 - Interrupted (acute GVHD resolved, then chronic GVHD developed)
 - De novo* (acute GVHD never developed)
 - Chronic GVHD flare (symptoms reactivated within 30 days of drug tapering or discontinuation)
- Platelet count at diagnosis of chronic GVHD (expressed as $\times 10^9/L$)
- KPS at time of diagnosis of chronic GVHD.
- Diagnosis was based on: histologic evidence / biopsy proven; clinical evidence; both; unknown.
- Current and past chronic GVHD treatments (ALG, ATG [for ALG, ATG, specify source: horse, rabbit, other]; azathioprine; glucocorticoids, systemic; glucocorticoids, topical; CsA; extra-corporeal photopheresis; etretinate; TAC; hydroxychloroquine;

Confidential

anti-CD25 [zenapax, daclizumab, anti-Tac]; campath; etanercept; infliximab; other *in vivo* monoclonal antibody; clofazimine; MMF; MPS; psoralen and ultraviolet A; SRL; EVL; thalidomide; ursodiol; other agent).

Concomitant baseline therapies, as defined in Section 5.3, will be recorded in the eCRF.

4.6 Extension Treatment Period inclusion criteria

For inclusion into the Extension Treatment Period of the study, all of the following inclusion criteria must be fulfilled. No waivers of any of the criteria for any subject are allowed:

1. Signed informed consent prior to initiation of any study-mandated procedure.
2. Subject has completed the 24 weeks of treatment of the Core Treatment Period and the EOT1 visit.
3. Subject has experienced disease progression 7 to 90 days after EOT1 visit, versus EOT1 chronic GVHD activity assessment, for at least one previously involved organ. Progression is per NIH Consensus Development Project response criteria and is defined in Section 6.3.2.
4. WOCBP, as defined in Section 4.3.1, must have a negative urine pregnancy test at enrollment visit EX-1, and at all prior visits, and must agree to undertake monthly scheduled urine pregnancy tests during the study and up to the protocol defined EOS.
5. WOCBP must agree to use acceptable MOC during the study and up to the protocol defined EOS.

4.7 Extension Treatment Period exclusion criteria

There are no exclusion criteria for the Extension Treatment Period. However:

- Study drug specific dose-reduction, interruption, or premature discontinuation criteria remain in force for the duration of the study. These are described in Section 5.1.10.
- Forbidden concomitant therapies remain in force for the duration of the study. These are described in Section 5.3.5.

5 TREATMENTS

5.1 Study treatment

The study treatment is the investigational drug ponesimod, administered during the Core and Extension Treatment Periods of the study.

In the Core Treatment Period, study treatment consists of a 5 mg ponesimod treatment period (from Days 1 to 28 including up-titration), 10 mg ponesimod treatment period (from Days 29 to 56 including up-titration) and a 20 mg treatment period (from Days 57 to day before EOT1).

In the Extension Treatment Period, study treatment consists of the subject's last tolerated dose administered throughout the Extension Treatment Period. The dose is either 5 mg, 10 mg, or 20 mg. The Extension Treatment Period is 96 weeks long, including up-titration, and starts with the enrollment visit EX-1 and ends with the EOT2 visit.

5.1.1 Investigational treatment: description and rationale

Ponesimod is supplied as its free base, in oral film-coated tablets at the doses of 2, 3, 4, 5, 6, 7, 8, 9, 10, and 20 mg. One tablet of ponesimod at any dose will be taken orally o.d.

Core Treatment Period

For this dose-escalation study, subjects will receive three treatment courses, with each treatment course studying one of the following ponesimod daily doses: 5, 10, and 20 mg.

This is the first clinical trial of ponesimod in subjects with chronic GVHD, and will assess PK, PD, safety and efficacy of 5, 10 and 20 mg of ponesimod. Initially, subjects enrolling in the study will be treated for 4 weeks with 5 mg ponesimod (6-day up-titration, 22 days at 5 mg), followed by treatment for 4 weeks with 10 mg of ponesimod (4-day up-titration, 24 days at 10 mg). For the remaining 16 weeks of the study the subjects will be treated with 20 mg ponesimod.

From past clinical trial experience, 20 mg ponesimod has displayed an optimal benefit-risk balance in subjects with MS and psoriasis. For these reasons, 20 mg has been chosen as the maximum dose to be studied in this clinical trial.

Extension Treatment Period

Subjects who completed the Core Treatment Period (i.e., not prematurely discontinued from study drug) may enroll in the Extension Treatment Period should their chronic GVHD worsen after stopping study drug at Week 24/EOT1 visit (as per eligibility criteria in Sections 4.6 and 4.7). Subjects will be up-titrated to their last tolerated ponesimod dose (prior to EOT1) and will receive ponesimod for 96 weeks, including up-titration.

5.1.2 Study treatment administration

5.1.2.1 *Subject study treatment diary*

Core Treatment Period

Subjects will be given a device to record every time ponesimod is taken. Details of the diary and instructions for completing it will be provided to the investigator. Site personnel will instruct the subject on how to complete the diary prior to administration of the first dose of study medication on Day 1 (Visit 2).

Extension Treatment Period

Confidential

Subjects will be given instructions on proper use of ponesimod (no device will be provided).

5.1.2.2 Titration

Core Treatment Period

A 6-day up-titration will occur during study Days 1–6 using a titration blister wallet, to reduce ponesimod first-dose effects. On-site subject monitoring will be required at enrollment on Day 1 [see Section 5.1.7]. A 4-day up-titration will occur during study Days 29–32 to gradually transition from the 5 mg to the 10 mg daily dose. The subject will have the dose escalated from 10 to 20 mg on Day 57 (without gradual up-titration). The first day of the 4-day up-titration (Day 29) and the Day 57 dose escalation do not require on-site monitoring. [See Table 3].

Table 3 Up-titration and dose-escalation schedule: Core Treatment Period

Treatment Course		Study Day	Ponesimod Daily Dose
1	6-day up-titration	1 (Enrollment)	2 mg (first dose given on-site with monitoring)
		2	2 mg
		3 and 4	3 mg
		5 and 6	4 mg
	5 mg daily	7 to 28	5 mg
2	4-day up-titration	29 (Week 4)	6 mg
		30	7 mg
		31	8 mg
		32	9 mg
	10 mg daily	33 to 56	10 mg
3	Dose escalation to 20 mg	57 (Week 8)	20 mg
	20 mg daily	58 to day before EOT1 (Week 24)	20 mg

EOT1 = End-of-Treatment for the Core Treatment Period

Extension Treatment Period

A 6- or 14-day up-titration will occur starting at Visit EX-1 using a titration blister wallet, to reduce ponesimod first-dose effects. On-site subject monitoring will be required at enrollment at Visit EX-1 [see Section 5.1.7]. The choice of the 6- or 14-day up-titration will depend on the targeted dose: 5 mg, 10 mg, or 20 mg. The targeted dose is the subject's previously tolerated ponesimod dose just prior to EOT1. [See Table 4].

Table 4 Up-titration schedule: Extension Treatment Period

- The following up-titration scheme using a titration blister wallet is applied if the ponesimod 5 mg dose is targeted.

6 day up-titration scheme		
Day(s)	Ponesimod Daily Dose	Given at site with monitoring
1 (Visit EX-1)	2 mg	Yes
2	2 mg	No
3 and 4	3 mg	No
5 and 6	4 mg	No
7 to EOT2	5 mg	No

- The following up-titration scheme using a titration blister wallet is applied if the ponesimod 10 mg dose is targeted.

14 day up-titration scheme		
Day(s)	Ponesimod Daily Dose	Given at site with monitoring
1 (Visit EX-1)	2 mg	Yes
2	2 mg	No
3 and 4	3 mg	No
5 and 6	4 mg	No
7	5 mg	No
8	6 mg	No
9	7 mg	No
10	8 mg	No
11	9 mg	No
12, 13, and 14	10 mg	No
15 to EOT2	10 mg	No

- The following up-titration scheme using a titration blister wallet is applied if the ponesimod 20 mg dose is targeted.

14 day up-titration scheme		
Day(s)	Ponesimod Daily Dose	Given at site with monitoring
1 (Visit EX-1)	2 mg	Yes

2	2 mg	No
3 and 4	3 mg	No
5 and 6	4 mg	No
7	5 mg	No
8	6 mg	No
9	7 mg	No
10	8 mg	No
11	9 mg	No
12, 13, and 14	10 mg	No
15 to EOT2	20 mg	No

Core and Extension Treatment Periods

Study drug dose up-titration, other than described above, is prohibited. Study drug dose reduction is permitted under some circumstances [see Section 5.1.10].

One tablet will be taken orally o.d., preferably in the morning, with or without food, and preferably at approximately the same time each day. The tablet will be swallowed as a whole. The last administration date and time of study drug before a visit and the administration date and time of study drug on the days of visits will be recorded in the eCRF.

5.1.2.3 Criteria to permit dose increases at Day 29 and Day 57 (Core Treatment Period)

Subjects may have daily doses up-titrated from 5 mg to 10 mg started on Day 29, or dose escalated from 10 mg to 20 mg on Day 57, if the following is true:

- Subject has not met the study-specific criteria for interruption, dose reduction, or premature discontinuation of study treatment, described in Section 5.1.10.
- Subject does not have an ongoing grade 2 adverse event at least possibly related to study drug.
- Subject took the correct scheduled study drug dose the day prior to the day of up-titration or dose escalation.
- Investigator has reviewed and approved of the results of the Day 29 and/or Day 57 pre-dose assessments specified in Table 1.

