	Visit window		± 7 days	± 7 days	± 7 days	+ 7 days
Extension Treatment inclusion/exclusion criteria*		X				
Chronic GVHD Activity Assessment, Form A and B*		X	X (Visit EX-4 only)	X	X	
Lee Symptom Scale*		X	X (Visit EX-4 only)	X	X	
Concomitant medications*		X	X	X	X	X
Physical examination*		X	X (Visit EX-4 only)	X	X	
Body weight*		X	X (Visit EX-4 only)	X	X	
Systolic/diastolic blood pressure*		X See Section 5.1.7	X (pre-dose)	X (pre-dose)	X	X
12-lead ECG (2)**		X See Section 5.1.7	X (pre-dose)	X (pre-dose)	X	X
Ophthalmological examination*			X (Visit EX-4 only)		X	
OCT (3)*			X (Visit EX-4 only)		X	
Spirometry*/DLCo*		X pre-dose	X (Visit EX-4 only) pre-dose	X pre-dose	X	X
Hematology**/Chemistry**/ Urinalysis		X pre-dose	X pre-dose	X pre-dose	X	X
Pregnancy test*/MOC* (5)		X urine	X urine	X urine (11)	X urine	X urine
PK and PD** sampling		X (PD only) pre-dose	X (PD only) (Visit EX-4 only) pre- dose	X (PD only) pre-dose	X (PD only)	X (PD only)
Study drug dispensing & accountability (6)**		X	X	X	X	
AEs & SAEs (7)*		X	X	X	X	X

*Data collected in the eCRF

**Electronically transferred to the sponsor

Confidential

Table 1 Visit and assessment schedule (continued)

Table notes

Day 1 (date of first study drug intake) is to be used as the reference date for the purpose of calculating the subsequent visit dates (and time windows).

- (1) Any chest X-ray that has been performed within 90 days prior to screening can be used (in this case, no need to repeat chest X-ray at screening).
- (2) In the event of a CTCAE grade 2 QTc elevation identified on 12-lead ECG (QTc 481–500 ms), a 12-lead ECG must be repeated 3 hours post dose. The subject is prematurely discontinued if the repeated QTcF > 500 ms.
- (3) OCT is performed at indicated visits plus any visit in case of visual symptoms suggestive of macular edema.
- (4) Investigator must review all test results prior to permitting subject to start the 4-day up-titration at Visit 3 and/or the dose escalation to 20 mg at Visit 4.
- (5) For women of child-bearing potential, the serum pregnancy test at Visit 1 must be performed at least 3 weeks before a urine pregnancy test at Visit 2. A second serum pregnancy may be performed instead of the urine test as early as 7 days after the first serum pregnancy test, and enrollment can begin as soon as the negative result is available. Assess and reinforce continued use of MOC for women of child-bearing potential at every visit.

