5.1.10 Specific dose-reduction, interruption, or premature discontinuation criteria

Ponesimod should be prematurely discontinued before initiating rescue IS therapy or other forbidden medications during the Core Treatment Period. Ponesimod should also be prematurely discontinued before initiating forbidden medications during the Extension Treatment Period. See Section 5.3.5.

Ponesimod-specific dose reduction, interruption, or premature discontinuation criteria are presented for a variety of conditions and scenarios grouped according to the following organ systems. These criteria apply during both the Core and Extension Treatment Periods:

- (1) Cardiovascular
- (2) Hematologic
- (3) Hepatobiliary
- (4) Immune/infection

- (5) Ocular
- (6) Reproductive/pregnancy
- (7) Respiratory

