5.1.10.3 Hepatobiliary

In case of abnormal liver tests or signs and symptoms suggestive of drug-induced liver injury, subjects will be closely observed, liver tests will be repeated, and ponesimod may need to be prematurely discontinued or interrupted.

The central laboratory will send alerts to the principal investigator and the sponsor whenever any of the following hepatobiliary laboratory abnormalities are recorded during the study:

- \geq Grade 2 elevation ALT ($> 3 \times \text{ULN}$)
- \geq Grade 2 elevation AST ($> 3 \times \text{ULN}$)
- \geq Grade 2 elevation blood bilirubin (same as TBL) ($> 1.5 \times \text{ULN}$)

The site will immediately contact the subject and ask him/her to return to the site within 72 hours, at the latest, to repeat the test by the central laboratory (unless the clinical situation mandates immediate local testing). An inquiry should be made about symptoms.

Should repeat testing confirm continuing abnormality, the following will apply:

Ponesimod must be prematurely discontinued for any of the following:

- Grade 4 ALT or AST elevation ($> 20.0 \times \text{ULN}$).
- Grade 4 blood bilirubin (same as TBL) elevation ($> 10.0 \times \text{ULN}$).
- Grade 2 or higher ALT or AST elevation ($> 3 \times \text{ULN}$) and (TBL $> 2 \times \text{ULN}$ or international normalized ratio [INR] > 1.5 ; corresponds to Hy's Law).
- Grade 2 or higher ALT or AST elevation ($> 3 \times \text{ULN}$) with the appearance of: fatigue, nausea, vomiting, right upper quadrant pain or tenderness, fever, rash, and/or eosinophilia ($> 5\%$).
- Grade 3 or higher ALT or AST elevation ($> 5.0 \times \text{ULN}$) during study Days 2–56 or study Days 149–168.
- Grade 3 or higher TBL elevation ($> 3.0 \times \text{ULN}$) during study Days 2–56 or study Days 149–168.
- Grade 3 or higher ALT or AST elevation ($> 5.0 \times \text{ULN}$) and subject is taking ponesimod 5 mg.
- Grade 3 or higher TBL elevation ($> 3.0 \times \text{ULN}$) and subject is taking ponesimod 5 mg.

Please see box “Monitoring for all subjects with confirmed \geq grade 2 AST, ALT, or TBL elevations”.

Confidential

Ponesimod is interrupted for any of the following:

- Grade 3 ALT or AST elevation ($> 5.0\text{--}20.0 \times \text{ULN}$) during study Days 57–148 or during the Extension Treatment Period.
- Grade 3 TBL elevation ($> 3.0\text{--}10.0 \times \text{ULN}$) during study Days 57–148 or during the Extension Treatment Period.

Procedure for interruption

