5.1.10.4 Immune/infection

Subjects must be prematurely discontinued from ponesimod at any time during the study in the event of an infection requiring discontinuation of treatment per investigator judgment.

In the event of an infection, the subject should be treated as clinically indicated and, if medically appropriate, study drug discontinued at the discretion of the investigator. In case of study drug discontinuation, adequate treatment needs to be provided, and the subject must be monitored until complete resolution of the infection.

If the infection resolves and the benefit/risk balance is considered acceptable for the subject to resume study treatment, ponesimod may be re-initiated at the discretion of the investigator. See Section 5.1.8 for re-initiation procedures.

Given ponesimod effects on lymphocytes, heightened vigilance is required for opportunistic infections, with particular attention to be paid to viral infections. However, investigators and physicians following subjects should also be alert to potential systemic infections caused by fungi and bacteria.

Table 5 highlights opportunistic infections common in patients at least 30 days following HSCT (and relevant for the patient population in this study).

Table 5 Common opportunistic infections in patients at least 30 days post-HSCT

Stage	Infections
Post-engraftment: approximately 30 to 100 days post-transplant	
 • Herpes viruses, especially CMV (Note: CMV causes pneumonia, hepatitis, and colitis and potentiates superinfection with opportunistic pathogens, particularly among patients with active GVHD) • Pneumocystis carinii • Aspergillus
Late phase: approximately 100 days post-transplant	
 • CMV • VZV • EBV-related post-transplant lymphoproliferative disease • CRV • Encapsulated bacteria (e.g., H. influenzae and S. pneumoniae).

Adapted from: CDC 2000

CMV = cytomegalovirus; CRV = community-acquired respiratory viruses; EBV = Epstein-Barr virus; GVHD = graft versus host disease; VZV = varicella zoster virus

If an opportunistic infection should occur despite appropriate and tailored infection prophylaxis and if, in the judgment of the investigator, the opportunistic infection does not respond as expected to anti-infectives, the subject must discontinue ponesimod and must be referred to an expert in infectious diseases for further examination and treatment.

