Appendix 5 Adverse events of special interest

AEs of special interest include the anticipated risks of treatment with ponesimod or the known class effects and will address the following safety areas:

- Effect on HR and rhythm related AEs (including adverse events related to hypotension)
- Cardiovascular related AEs
- Hypertension related AEs
- Stroke related AEs
- Seizure related AEs
- Hepatobiliary disorders / liver enzyme abnormality related AEs
- Pulmonary related AEs
- Macular edema related AEs
- Infection related AEs
- Herpetic infections related AEs
- Skin malignancy related AEs
- Non-skin malignancy related AEs

A list of AEs of special interest (MedDRA preferred terms) will be defined in the SAP.

Confidential

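### The adverse-event condition for the Day 29 and Day 57 dose increases names grade 2 only, so as written a related grade 3 or 4 event that meets no Section 5.1.10 rule is not a mandatory bar

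*Combined protocol and SAP*

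**What the plan says.** Section 5.1.2.3 sets four conditions for a dose increase at Day 29 or Day 57; the synopsis letters them (a) to (d).

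- (a) No Section 5.1.10 criterion for interruption, dose reduction or discontinuation has been met.
- (b) "Subject does not have an ongoing grade 2 adverse event at least possibly related to study drug".
- (c) Study drug was taken on the preceding day.
- (d) The investigator has reviewed and approved the pre-dose assessments.

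Condition (b) has the same wording in both places, so neither corrects the other.

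Section 5.1.10 describes its own content as criteria "presented for a variety of conditions and scenarios grouped according to the following organ systems": cardiovascular, hematologic, hepatobiliary, immune/infection, ocular, reproductive and respiratory. The infection rule (Section 5.1.10.4) carries no grade. It requires discontinuation "in the event of an infection requiring discontinuation of treatment per investigator judgment".

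**The concern.** A toxicity gate should become stricter as toxicity worsens. This one, followed to the letter, makes a moderate related event a compulsory hold and leaves a severe or life-threatening one to judgment, unless that event happens to meet an organ-specific rule. What is at stake is subject safety during escalation, in the first trial of ponesimod in chronic GVHD (Section 5.1.1) and in subjects already on background immunosuppression. Infection is the clearest case: Appendix 5 lists "Infection related AEs" among the events of special interest, yet the infection rule in Section 5.1.10.4 has no grade threshold.

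**Working it through.** No arithmetic applies. The check sets the relevant texts side by side.

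**1. Does a bare grade mean that grade and above in this protocol?** The usage in the document says no.

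- Section 5.1.10.3 marks open ranges explicitly in nine bulleted criteria: three with a greater-or-equal sign before grade 2 (the ALT, AST and bilirubin alerts), two in the form "Grade 2 or higher ALT or AST elevation", and four that put the same qualifier on grade 3 (two for transaminases, as in "Grade 3 or higher ALT or AST elevation", and two for bilirubin). 3 + 2 + 4 = 9.
- Bare grades are used for closed levels. The interruption rule headed "Grade 3 ALT or AST elevation" is bounded at > 5.0 to 20.0 × ULN. Table 1, note (2), which begins "In the event of a CTCAE grade 2 QTc elevation identified on 12-lead ECG", gives the range as 481 to 500 ms.
- Within Section 5.1.10.3 the open and closed forms of grade 3 lead to different actions (discontinue and interrupt, respectively). The distinction is therefore operative, and a careful site has textual reason to read (b) literally.

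**2. Does condition (a) catch the higher grades?** Only some of them.

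- Caught: for example, confirmed ALT or AST above 5 × ULN, QTcF above 500 ms, and confirmed neutrophils below 0.5 × 10⁹/L.
- Not caught: a related grade 3 infection that the investigator does not judge to require discontinuation.
- Not caught: a related severe respiratory event that does not meet all three spirometry conditions in Section 5.1.10.7 together (FEV₁ down more than 10% from baseline, FEV₁ below 60% predicted, FEV₁/FVC below 0.7). That section requires careful evaluation but states no hold.
- Not caught: events in organ systems with no rule, such as a severe related headache.

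**3. Does condition (d) catch them?** It can, but by judgment. Table 1 has an adverse-event row. Sections 8.2.2 and 8.2.3 list adverse-event recording at Weeks 4 and 8. The introduction to Section 8 says that assessments at these visits are made before dosing. Adverse-event status is therefore plausibly within the sign-off, although Table 1 does not mark that row as pre-dose and note (4) speaks of test results. Condition (d) states no grade.

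**4. Result of the literal rule.**

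| Ongoing related event, no Section 5.1.10 rule met | (a) | (b) | Mandatory grade-based bar? |
|---|---|---|---|
| Grade 2 | satisfied | fails | yes |
| Grade 3 or 4 | satisfied | satisfied | no |

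**5. A side effect of the grading rules.** Section 10.1.2 does not require an event to be re-graded when it eases. An event that began at grade 3 and improved to grade 2 may still be recorded as grade 3, and so fall outside a bar tied to the recorded grade 2.

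**The case against.** The strongest reply is that nobody would apply the clause this way. Escalation is optional throughout. Condition (d) is a compulsory sign-off: without the investigator's approval the dose does not rise. Section 5.1.6 permits interruption for an adverse event. Section 5.1.9 tells the investigator to stop the drug when continuing is against the subject's interests. Grade 4 events, and events requiring inpatient hospitalization, are serious adverse events reportable within 24 hours. The Study Monitoring Committee reviews each subject's toxicity, and the sponsor reviews safety continuously. For the gap to matter, an investigator would have to attribute a severe ongoing event to ponesimod, decide that the drug need not stop, and then approve a higher dose.

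It can also be argued that (b) was drafted to add milder events to those already caught by (a). In the QTc and transaminase examples a stricter rule does sit above the named grade.

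Most of this stands, and it is why the point is minor. Two things do not follow from it. None of these safeguards requires a hold at grade 3 or 4. And reading (b) as a supplement to (a) works only where (a) has a rule, which it does not for every organ system or, in the case of infection, for any grade.

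A reader might infer that the Day 57 step is especially exposed because on-site monitoring is waived there. The documents do not support that. The waived monitoring is the hourly cardiac observation used at initiation and re-initiation (Section 5.1.7), not surveillance for ongoing adverse events. The Week 8 visit has pre-dose ECG, blood pressure, spirometry, DLco and laboratory tests that the investigator must review first.

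**Conclusion.** The wording is wrong as written, and the consequence is minor. Condition (b) makes an ongoing related grade 2 event a mandatory bar and does not do the same for an ongoing related grade 3 or 4 event that meets no Section 5.1.10 rule. This rests on reading a bare grade as a single level, which is how the protocol uses it elsewhere. The intent was almost certainly grade 2 or higher.

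Three stronger readings should be resisted.

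- The plan does not direct escalation in subjects with severe toxicity. It leaves that decision to judgment.
- No frequency can be given. The documents report no rate of related grade 3 or 4 events outside Section 5.1.10. Multiplying subjects by two gates would not help either: a subject held at 5 mg on Day 29 never reaches the 10-to-20 mg step, and Sections 5.1.8, 5.1.10.2 and 5.1.10.7 bar later escalation for some others who continue.
- No effect on the primary pharmacodynamic analysis is claimed.

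**What to change.** In Section 5.1.2.3 and in the matching synopsis item (b), insert *or higher* directly after *grade 2*. Leave the rest of the clause unchanged.

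This costs two words in two places by amendment. No new data are needed, because the grade and relationship of every adverse event are already assessed. The downside is that an unknown, probably small, number of subjects may be held at a lower dose. They could include some whose clinically significant lymphocyte decreases are recorded as related adverse events (Section 10.1.1 counts such laboratory findings as adverse events), although lymphocyte reduction is the drug's intended effect.
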